15.3.12 Predictors of Therapeutic Response

Exploratory analysis, using linear regression and logistic regression models, will be performed to identify baseline variables associated with reduced PTS. Within the PCDT group, differences in endovascular technique will be described and associations with outcomes will be explored. A history of previous ipsilateral DVT and any previous DVT will be included as analysis variables.

15.4 Additional Analysis Issues

15.4.1 Confounding

Stratification at randomization for the extent of DVT and Clinical Center and the standardization of the use of standard DVT therapy (Section 12.5) will reduce the potential for confounding. However, in addition to the unadjusted analysis described above, an adjusted analysis of the study outcomes comparing treatment Arms will be performed using multivariable regression analysis (linear regression for continuous outcomes, logistic regression for binary outcomes) that controls for the following baseline variables as main effects: age (continuous), gender (female vs. male), ethnicity (Hispanic/Latino vs. other), race (American Indian/Alaskan Native, Asian, Black, Hawaiian/Pacific Islander vs. White), body-mass index, employment status, previous ipsilateral DVT, inpatient (yes, no), duration of leg symptoms, extent of DVT at presentation (iliofemoral vs. femoropopliteal), symptom severity at presentation, and Clinical Center.

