3 STUDY DESIGN

This is an NIH-funded, Phase III, multicenter, randomized, open-label, assessor-blinded, parallel two-arm, controlled clinical trial. 692 subjects with symptomatic proximal DVT that involves the iliac, common femoral, and/or femoral vein will be randomized in a 1:1 ratio to receive either adjunctive PCDT (with rt-PA) + standard DVT therapy or standard DVT therapy alone. Subjects will be enrolled over 4.5 years in 30-60 U.S. Clinical Centers, and followed for 24 months. The study will take 6.5 years to complete. **Appendix 1** outlines the trial's organizational structure.

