15 STATISTICAL METHODS

15.1 Sample Size Calculation

The goal of the ATTRACT Trial is to determine if adjunctive PCDT (Experimental Arm), compared with optimal standard DVT therapy alone (Control Arm), reduces the 2-year occurrence of PTS in subjects with symptomatic proximal DVT. Based on previous studies (2-5), 30% of subjects in the Control Arm are expected to have PTS within 24 months of DVT diagnosis. Based on the expected success of PCDT at restoring venous patency and reductions of PTS that were achieved with thrombolytic therapy in earlier studies (33,34,42,51,52,139), we hypothesize that PCDT will reduce the risk of PTS by at least 33%. Accepting a 5% chance of incorrectly concluding that there is a difference in the proportion of subjects with PTS at 24 months with PCDT (α error=0.05; two-sided), and the requirement that the study has an 80% chance (β error=0.2) of detecting a true difference if PCDT truly reduces PTS by 33%, 311 subjects in each group must be studied (based on the Fisher's exact test).

In recently completed studies of long-term treatment for unprovoked VTE coordinated by the DCC, loss to follow-up or death occurred in 2.5% during 2 years follow-up (140), and in 3.4% during mean follow-up of 2.4 years (141). We therefore expect no more than 5% of randomized subjects to be lost to follow-up at 24 months. However, to ensure that statistical power will not be compromised, we will assume that as many as 10% of randomized subjects (double the maximum expected) will not complete the 24-month assessment. Therefore, we plan to randomize 346 subjects to each group, yielding a total study sample size of **692 subjects**.

For the secondary analyses, 692 subjects will provide approximately 88% power to detect an effect size of 0.25 with continuous outcomes. QOL changes from baseline: This translates into the ability to detect a difference of 1.25 in the VEINES-QOL change scores, and 2.5 in the SF-36v2 PCS and MCS change scores (change of 4 points is clinically important for all 3 scales).

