PTS severity on Villalta PTS Scale: A difference as small as 1.25 units can be detected (5-point gradations define severity categories) (98, 111). Ultrasound outcomes: Assuming a 50% risk of deep venous reflux in the Control Arm and 10% inflation for losses due to withdrawal, death, or inadequate exams (rare), 142 subjects will provide 80% power to detect a 50% relative risk reduction for this outcome (alpha = 0.05, two-sided). 128 evaluable subjects will provide 80% power to detect effect sizes of 0.5 for reflux and obstruction on the continuous VSDS scales.

Regarding safety, we will perform a descriptive analysis of the rates of major bleeding and symptomatic PE in the two study Arms. These events are expected to occur infrequently (2% for major bleeding at 10 days and for symptomatic PE at 3 months) in the Control Arm. With 311 evaluable subjects per arm, if 2% of each group experiences an outcome, the 95% confidence interval on the difference of 0% will include an absolute decrease or increase of 2.4%.

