15.2 Primary Analysis

The primary efficacy analysis is a comparison of the proportion of subjects in each Arm who have developed PTS, defined as a total score of \geq 5 in the limb ipsilateral to the index DVT on the Villalta PTS Scale (or an ulcer) at the 6-month follow-up visit, or subsequently during the 24 months after randomization. A stratum-adjusted Cochran-Mantel-Haenszel test will be used. All testing will be two-sided, and a p-value of 0.05 or less will be considered statistically significant.

Subjects will also be counted as having PTS if they underwent an unplanned endovascular intervention (PCDT or another intervention) for the treatment of severe symptomatic venous disease in the index leg more than 6 months after randomization and either a) they had a total score of \geq 5 on the Villalta PTS Scale that was performed immediately preceding that intervention, or an ulcer; or b) the Villalta PTS Scale was not performed at that time.

Irrespective of any subsequent post-randomization intervention, all patients will be counted in the treatment arm to which they were originally randomized, per the intention-to-treat principle.

Two data sets will be considered:

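### Section 15.4.1 enters 30-60 Clinical Centers as main effects in the adjusted logistic models, which exaggerates the supportive PTS estimate and leaves the model without a finite joint fit for outcomes as rare as 2%

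*Protocol*

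**What the plan says.** Section 15.4.1 of the protocol adds an adjusted comparison of the arms to the main analyses. It covers the study outcomes generally, with linear regression for continuous outcomes and "logistic regression for binary outcomes) that controls for the following baseline variables as main effects". Twelve variables follow. Race has four categories set against White, and the list ends with "symptom severity at presentation, and Clinical Center". The section mentions no random effect, conditioning on center, pooling of small centers, penalization or minimum number of events.

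The number of centers is in Section 3: "Subjects will be enrolled over 4.5 years in 30-60 U.S. Clinical Centers". Section 15.1 gives the planning rates. For PTS, "30% of subjects in the Control Arm are expected to have PTS within 24 months of DVT diagnosis", with a hypothesized relative reduction of 33% and 311 evaluable subjects per arm. For safety in the Control Arm, "These events are expected to occur infrequently (2% for major bleeding at 10 days and for symptomatic PE at 3 months").

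The primary test in Section 15.2 is a stratum-adjusted CMH test. Sections 15.3.1 to 15.3.3 use the same test for symptomatic VTE, bleeding and mortality.

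**The concern.** A logistic model fitted by maximum likelihood behaves badly when the number of nuisance terms grows with the number of small centers. Each center intercept is estimated from few subjects, and the error passes into the treatment coefficient and pushes it away from zero. Enrolling more subjects by opening more centers of the same size does not cure this. Centers in which nobody, or everybody, has the event have intercepts that run off to infinity.

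For PTS, the adjusted estimate would be reported beside the primary result. If it looks stronger than the CMH result, readers may take this as confirmation after control for confounding, when part of it is sparse-data bias. The error favors PCDT whenever PCDT has a true benefit. For bleeding, the main expected harm of rt-PA, an adjusted odds ratio from such a model would be unstable and would rest on a part of the trial that nobody chose.

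**Working it through.** **The plan's own figure.** With 30% versus 20%, two-sided alpha 0.05 and 311 per arm, full enumeration gives a power of 0.8004 for Fisher's exact test. 311 / 0.90 = 345.6, so 346 per arm and 692 in total. Section 15.1 is reproduced.

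**Number of terms.** Eleven variables other than center: race takes 4 indicators and the other ten are counted at 1 each, so 14. (One term each for employment status and symptom severity is an assumption; more would make matters worse.) Treatment adds 1 and center adds 29 to 59.

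- 30 centers: 14 + 1 + 29 = 44
- 60 centers: 14 + 1 + 59 = 74

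**PTS events per term.** 311 × 0.30 + 311 × 0.20 = 93.3 + 62.2 = 155.5. Then 155.5 / 44 = 3.5 and 155.5 / 74 = 2.1.

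**Size of the PTS bias.** True log odds ratio: ln(0.20/0.80) − ln(0.30/0.70) = −1.386 + 0.847 = −0.539, an odds ratio of 0.583. Four simulations of the model with center indicators, each with 622 subjects where stated, gave these mean log odds ratios:

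| Simulation | 30 centers | 60 centers |
|---|---|---|
| A: 600 runs per setting, equal or skewed center sizes, covariates prognostic or not | 7-9% too large | 12-16% too large |
| B: 600 runs, skewed sizes, center SD 0.4 on the logit | −0.584 (8%) | −0.602 (12%) |
| C: 150 runs, skewed sizes, center SD 0.4 | −0.581 (8%) | −0.610 (13%) |
| D: further simulation | −0.57 (6%) | −0.61 (13%) |

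At 45 centers simulation A gave 12-14%. Across all four, the mean log odds ratio lies between −0.57 and −0.63, which is an odds ratio of 0.57 to 0.53.

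**Is center the cause?** In C, conditional logistic regression stratified on center, fitted to the same data, gave −0.553 (30 centers) and −0.555 (60). In D it gave about −0.54. In B, leaving out the center indicators gave −0.541 and −0.529. The Monte Carlo standard error of the center-indicator means in C is about 0.018. Conditional logistic regression targets the same center-specific odds ratio, so the gap between the two fits is not the ordinary difference between a conditional and a marginal odds ratio.

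**Under no effect.** In 1,500 runs each at 30 and 60 centers (25% in both arms), the mean coefficient was close to 0 (0.010 and −0.005). Rejection at nominal 5% was 6.0% and 6.1%. A model without center indicators and sparse race and ethnicity terms rejected in 4.9-5.5%. The Monte Carlo standard error at 5% is √(0.05 × 0.95 / 1500) = 0.56 percentage points, so this excess is small.

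**Rare outcomes.** At 2% in both arms, 692 × 0.02 = 13.8 events. 13.8 / 44 = 0.31 and 13.8 / 74 = 0.19 events per term. On average 67% (30 centers) to 80% (60 centers) of centers had no event. Separation, meaning no finite joint maximum-likelihood estimate, occurred in every run, and also with 4% or 6% in the PCDT arm.

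The treatment coefficient alone was then checked in 120 runs per setting:

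| Control / PCDT rate | Centers | Coefficient finite | Subjects it rests on | Median (true) |
|---|---|---|---|---|
| 2% / 2% | 30 | 98% | 48% | −0.02 (0) |
| 2% / 2% | 60 | 99% | 32% | 0.00 (0) |
| 2% / 4% | 30 | 100% | 61% | 0.82 (0.71) |
| 2% / 4% | 60 | 100% | 44% | 0.90 (0.71) |
| 1% / 2% | 30 | 98% | 39% | 1.04 (0.70) |
| 1% / 2% | 60 | 91% | 24% | 0.94 (0.70) |

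The PCDT rate of 4% and the 1% / 2% pair are assumptions; the protocol gives only the Control Arm 2%. With 10 events the unadjusted median is itself unsteady (0.85 and 0.71 in the last two rows), so the 2% / 4% rows are the better guide to the bias.

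**The case against.** The strongest reply is that this is detail for the SAP. Section 15.4.1 never says that center effects are fixed or coded as indicators; main effects may simply mean no interactions, and a random center intercept would satisfy that. Section 15.6 promises a detailed SAP approved before unblinding. Fixed is indeed an inference. But the section goes beyond a general intention: it names the model, the outcomes and the covariate list, and puts a 30-60-level factor in that list on the same footing as age and gender. The ordinary reading is the model tested here, so the text needs correcting.

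The second reply is that safety is already handled. Section 15.1 calls the bleeding and PE analysis descriptive, and Sections 15.3.1 to 15.3.3 use CMH tests. This largely stands. What remains is that Section 15.4.1 extends the adjusted model to the study outcomes and exempts none of these.

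A reader might infer three stronger things that the documents do not support:

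- That the trial's main conclusion is biased. It is not: the primary test is CMH, and this model is supportive.
- That the treatment effect on bleeding or PE cannot be estimated. Separation concerns the joint fit; the treatment coefficient was finite in 91-100% of runs.
- That the same failure is shown for death, any bleeding or events out to 24 months. The protocol gives no rates for these.

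**Conclusion.** The point holds for the supportive adjusted analysis. Followed as written, Section 15.4.1 exaggerates a true PTS effect by roughly 6-16% on the log-odds scale. The odds ratio moves further below 1, from 0.583 to about 0.53-0.57. With no true effect there is no bias, only rejection of about 6% instead of 5%. For outcomes at 2% the specified model has no finite joint fit. Its treatment coefficient is usually finite but imprecise and rests on 24-61% of subjects (32-61% if the assumed 1% / 2% case is left out). At an assumed 2% versus 4% it is exaggerated, with a median of 0.82-0.90 against 0.71.

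The term and event counts follow from the protocol. The size of the bias rests on assumed covariate prevalences, center-size distributions and, in some runs, center variation; it was in the same direction in every setting tried. The case for changing the text is the modest but systematic PTS bias and the unsuitability of the full model for rare events.

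**What to change.** Amend Section 15.4.1 in two places, and carry the wording into the SAP before unblinding.

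1. For binary outcomes, handle Clinical Center by conditional logistic regression stratified on center, or by a random center intercept, keeping DVT extent and the other covariates. Conditioning removed most of the excess in the checks above; the random intercept was not simulated here.
2. State that binary outcomes with too few events for the covariate list are left out of the multivariable model and reported only by the stratum-adjusted comparison already planned in Sections 15.3.1 to 15.3.3. This is to be expected for early major bleeding and PE, and for death if its count is low.

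The cost is wording; both methods are available in the SAS and R software named in Section 15.4.3. The downside is small: conditional and random-intercept estimates drop or shrink information from small centers, and no covariate-adjusted estimate is given for rare events. The primary analysis and sample size do not change.

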15.4.2 Missing Data

The training of study personnel, the use of electronic Case Report Forms that have been pilot tested for clarity, and the precautions noted in Section 14.3 are expected to minimize the occurrence of missing data. If a subject misses a visit but can be reached by phone within 1 month of the visit, the five patient-reported symptom questions of Villalta PTS Scale will be asked over the phone. From these responses, the total (symptoms plus signs) Villalta score will be estimated using a simple imputation algorithm. The same algorithm will be used for other situations in which the Villalta PTS assessment is only partially completed. From the data in our recently completed study (145), the correlation between the Villalta symptom and total scores was found to be extremely high (between 0.85 and 0.90). Similarly, the VEINES and SF-36v2 guestionnaires will also be administered by phone in the rare situations when the subject is unable to attend clinic. For missed visits, the total Villalta score, the SF-36 component scores, and the VEINES Sym and QOL component scores will be estimated using multiple imputation (MI) methods, but only for the sensitivity analysis. For all other outcomes, no missing data imputation will be undertaken. For missing baseline data items that serve as covariates, iterative methods such as the Markov Chain Monte Carlo (MCMC) method will be employed to solve this problem. The possibility of non-ignorable missing outcomes will be investigated in exploratory analyses.

15.4.3 Software

All data checking/manipulation and most of the analysis and graphics will be undertaken using SAS (Cary, NC) software. In addition, Cytel's StatXact software will be used for all exact

71

nonparametric analysis; the R open-source software will be used for any non-standard statistical analysis and to produce plots; the Minitab (State College, PA) statistical and graphics software will also be used to produce plots. The latest available versions will be used.

15.5 Interim Analyses and Stopping Guidelines

All relevant data and summaries will be provided to the Data Safety Monitoring Board (DSMB) by the DCC (Section 17.4). The DSMB will review the frequency of adverse safety outcomes, particularly symptomatic VTE and major bleeding, at intervals that it determines (146,147). Initially, such reviews will be done without knowledge of allocation, but the DSMB can request unblinding at any stage. Based on an overall assessment of risk and benefit, the DSMB can recommend premature stopping of the study to the NHLBI at any time.

We do not anticipate early stopping because of superior efficacy of PCDT because: (1) the primary outcome for efficacy reflects symptoms rather than survival; and (2) it is most improbable that evidence of superior efficacy of PCDT of a sufficient size to change clinical practice can be obtained without enrollment of nearly the entire planned sample size (148,149).

15.6 Statistical Analysis Plan

A detailed statistical analysis plan will be prepared by the study statistician and submitted to the Steering Committee and DSMB for review and approval prior to unblinding and database lock.

16 INVESTIGATOR RESPONSIBILITIES

16.1 Study Initiation

Before enrollment of the first subject at each Clinical Center, the following documents must be on file with the ATTRACT Clinical Coordinating Center at Washington University:

- Original U.S. FDA Form 1572, signed by the site principal investigator. The names of all co-investigators at the Clinical Center must also appear on this Form.
- Current curriculum vitae of the principal investigator and all co-investigators.
- Current, dated Institutional Review Board (IRB) membership list.
- Written documentation of IRB protocol approval (protocol number/title and approval date) and informed consent document (protocol number/title and approval date).
- A copy of the IRB-approved informed consent document. The informed consent document must be reviewed by the study Principal Investigator prior to IRB submission.
- A copy of the IRB-approved authorization for Protected Health Information (HIPAA
requirement). This may be integrated into the patient informed consent document.

- Written documentation of IRB review and approval of any advertising materials that will be used for subject recruitment to the study.
- Current laboratory certification (Clinical Laboratory Improvement Amendments (CLIA) and the College of American Pathologists [CAP]) of the institution listed on the Form 1572
- Medical Therapy Committee certification of anticoagulation monitoring plans and medical co-investigator credentials
- Interventions Committee certification of endovascular co-investigator credentials
- Ultrasound Core Laboratory certification to perform compression ultrasound exams

16.2 Study Completion

The following data and materials must be on file at the Clinical Coordinating Center at Washington University before the study can be considered complete or terminated:

- Laboratory findings, clinical data and test results from screening through end of followup.
- Case Report Forms, properly completed.
- Copies of protocol amendments and IRB approvals, if appropriate.
- Review of final visit checklist.
- Copy of study termination letter sent to the IRB.
- All regulatory documents (CV for each investigator, U.S. FDA Form 1572 for each Center)

16.3 Institutional Review Board Approval

The protocol, informed consent document, and supporting information must be approved by the IRB before study initiation. The study will be conducted in accordance with the requirements of the FDA, NHLBI, applicable national and local health authorities, and participating institutions' IRBs. The Clinical Center principal investigator is responsible for keeping the IRB apprised of study progress and protocol changes as deemed appropriate, at a minimum of once a year. The Clinical Center principal investigator must also notify his/her IRB of all unexpected SAEs. Some IRBs have other AE requirements to which investigators are expected to adhere. Investigators must immediately forward to their IRB any written safety update provided by the Principal Investigator (i.e. IND Safety Report, safety amendments, updates to the study protocol).

Changes or additions to the study protocol or informed consent document at a Clinical Center must be approved in writing by the ATTRACT Principal Investigator and the Center's IRB.

16.4 Informed Consent

Template informed consent documents will be provided to each site. The final IRB-approved document must be provided to the study Principal Investigator, including the protocol version and date. The informed consent document must be signed by the subject or his/her legally authorized representative before participation in the study. A copy of the informed consent document must be provided to the subject or his/her legally authorized representative. If applicable, it should be provided in a certified translation of the local language.

Signed consent forms must remain in each subject's study file and be available for verification by Clinical Coordinating Center personnel at any time. Documentation of the date informed consent was obtained and a notation that a signed copy was given to the subject should be recorded. The informed consent process must always be conducted in a non-coercive manner, and should be consistent with the FDA regulation 21CFR, Part 50.

16.5 Study Monitoring Requirements

Site monitoring visits will be routinely conducted by authorized representatives of the Principal Investigator to inspect study data, informed consent forms, subjects' medical records, and Case Report Forms, pursuant to U.S. GCPs and other federal and local regulations. The Clinical Center principal investigator will permit authorized representatives of the FDA, NHLBI, Washington University, and local health authorities to inspect relevant facilities and records.

16.6 Case Report Forms

Web-based electronic CRFs will be provided to the Clinical Centers by the Principal Investigator and DCC. All CRFs should be filled out completely by the study coordinator or investigators. The CRFs must be reviewed by the site investigator prior to submission to the DCC. CRFs should be completed in a neat, legible manner to ensure accurate interpretation of the data.

